1. INTRODUCTION

1.1. Background

A novel coronavirus, SARS-CoV-2, has been identified as the cause of the global pandemic of COVID-19. Children of any age can get COVID-19 {Zimmermann 2020} and the incidence in children has been found to be similar to that in adults {Dawood 2022}. The prevalence of SARS-CoV-2 infection was initially reported to be low, with children and adolescents to represent approximately 1% to 2% of total cases, but the prevalence has increased over time, possibly related to increased testing rates {Nikolopoulou 2022}. As of January 2023, 17.2% of cases in the United States (US) were children from 0 to 17 years of age; with 3.6% cases in the age group 0-4 years, 6.5% cases in the age group 5-11 years, 4.5% cases in the age group 12-15 years, and 2.6% cases in the age group 16-17 years {Centers for Disease Control and Prevention 2022}. In a study conducted in school-aged children in the United Kingdom, median illness duration was longer for children aged 12 to 17 years (7 days) than children aged 5 to 11 years (5 days), with 4.4% of children having an illness duration of at least 28 days and longer duration occurring more commonly in older than younger children (5.1% vs 3.1%, respectively) {Molteni 2021}. Further, in addition to increased prevalence, the overall incidence of SARS-CoV-2 infection and COVID-19-related hospitalizations among children has increased over the course of the pandemic with successive SARS-CoV-2 waves and the emergence of unique variants {Ben-Tov 2022} {Marks 2022}. The percentage of intensive care unit admissions among hospitalized children is comparable to that for hospitalized adults with COVID-19 and hospitalization rates in the US associated with COVID-19 are higher among unvaccinated children than those who are vaccinated {Shi 2022} {Siegel 2021}. Both children and adults present with similar viral loads irrespective of hospitalization or symptom status {Madera 2021}, with fever and cough reported as the most common symptoms {European Center for Disease Prevention and Control 2022} {Nikolopoulou 2022}. Although children with COVID-19 are frequently asymptomatic or have symptoms that are reported as mild or moderate, symptoms can include nausea/vomiting, and upper respiratory complications {Swann 2020}, {Gotzinger 2020}, {Liguoro 2020}, {Zimmermann 2020}. The signs and symptoms of COVID-19 in children may overlap significantly with other respiratory and enteric viral infections. However, as in adults, COVID-19 can result in severe disease in children, leading to respiratory failure and acute respiratory distress syndrome {Bhalala 2022}. Other symptoms in children include gastrointestinal symptoms, sore throat/pharyngitis, shortness of breath, myalgia, rhinorrhea/nasal congestion, and headache, consistent with symptoms observed in adults. Furthermore, underlying conditions such as CCI [REDACTED], CCI [REDACTED] and CCI [REDACTED] children as well as adults to more severe COVID-19 disease; prematurity in infants is also a risk factor for severe disease {Fernandes 2021} {Kompaniyets 2021} {Tsankov 2021} {Uka 2022}.

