3.3. Protocol-Specific Discontinuation Criteria

3.3.1. Criteria for Early Discontinuation for the Individual Participants

3.3.1.1. Criteria for Early Discontinuation for the Individual Participants From Study Intervention

Study drug will be discontinued in the following instances:

- Any SAE suspected to be related to study drug.
- Any \geq Grade 3 AE suspected to be related to study drug.
- An AE, or worsening of clinical condition requiring clinical intervention, that would, in the judgment of the investigator, affect assessments of clinical status to a significant degree.
- Any \geq Grade 3 clinically significant laboratory abnormality (if confirmed by repeat testing) suspected to be related to study drug.
- eGFR < 50 mL/min/1.73 m² (≥ 1 year of age) using the Bedside Schwartz formula.
- Alanine aminotransferase (ALT) $\geq 5 \times$ upper limit of normal (ULN).
- Bilirubin $\geq 2 \times$ ULN ($\geq 3 \times$ ULN for participants with Gilbert's syndrome).
- Unacceptable toxicity, as defined in Section [7.7](#), or toxicity that, in the judgment of the investigator, compromises the ability to continue study-specific procedures or is considered not to be in the participant's best interest.
- Participant request to discontinue for any reason.
- Participant noncompliance with the study protocol.
- Pregnancy (refer to Appendix [11.4](#)).
- Discontinuation of the study by sponsor.
- Creatinine level above the thresholds described in [Table 3](#) if < 1 year of age.

Table 3. Creatinine Value Cutoff by Age Group

Gestational age	Chronological age	Creatinine Value Cutoff in mg/dL
≥ 24 to ≤ 27 weeks	0 to < 28 days	CC1
≥ 28 to ≤ 29 weeks	0 to < 14 days	CC1
≥ 30 to < 32 weeks	0 to < 7 days	CC1
	≥ 7 days to 1 month	CC1
	≥ 1 to < 2 months	CC1
	≥ 2 months to < 1 year	CC1
≥ 32 weeks	0 to < 2 days	CC1
	≥ 2 to < 7 days	CC1
	≥ 7 days to 2 months	CC1
	≥ 2 months to < 1 year	CC1

* Creatinine values CC1

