4.2. Inclusion Criteria

Participants must meet all of the following inclusion criteria to be eligible for participation in this study:

- 1) Participant or legal guardian willing and able to provide written informed consent prior to performing study procedures. Participants will provide assent, if possible, in accordance with local requirements and investigator's discretion.
- 2) Aged < 18 years who meet one of the following weight criteria and gestational age (GA) criteria where applicable (where permitted according to local law and approved nationally and by relevant IRB or IEC):
 - a) Cohort 1: ≥ 6 years to < 18 years and weight ≥ 40 kg
 - b) Cohort 2: ≥ 6 years to < 18 years and weight ≥ 20 kg to < 40 kg
 - c) Cohort 3: ≥ 2 years to < 18 years and weight ≥ 12 kg to < 20 kg
 - d) Cohort 4: ≥ 28 days to < 18 years and weight ≥ 3 kg to < 12 kg
 - e) Cohort 5: ≥ 14 days to < 28 days of age, GA ≥ 37 weeks and weight ≥ 2.5 kg
 - f) Cohort 6: 0 days to < 14 days of age, GA ≥ 37 weeks and birth weight ≥ 2.5 kg
 - g) Cohort 7: 0 days to < 56 days of age, GA < 37 weeks and birth weight ≥ 1.5 kg
- 3) SARS-CoV-2 infection confirmed by polymerase chain reaction (PCR) or an alternative molecular diagnostic assay ≤ 5 days before screening.

- 4) Initial onset of COVID-19 signs/symptoms \leq 5 days before screening with \geq 1 sign/symptom such as fever, cough, fatigue, shortness of breath, sore throat, headache, myalgia/arthralgia present at screening.
- 5) Presence of \geq 1 characteristic or underlying medical condition associated with an increased risk of developing severe illness due to COVID-19, including:
 - a) CCI [REDACTED]
 - b) CCI [REDACTED]
 - c) CCI [REDACTED]
 - d) CCI [REDACTED]
 - e) CCI [REDACTED]
 - f) CCI [REDACTED]
 - g) CCI [REDACTED]
 - h) CCI [REDACTED]
 - i) CCI [REDACTED]

4.3. **Exclusion Criteria**

Participants who meet *any* of the following exclusion criteria are not eligible to be enrolled in this study:

- 1) Anticipated access to and use of authorized or approved COVID-19 therapies during the current COVID-19 illness $<$ 5 days after screening (therapies including but not limited to nirmatrelvir/ritonavir, molnupiravir, intravenous RDV, monoclonal antibodies).
- 2) Vaccination for SARS-CoV-2 or self-reported history of SARS-CoV-2 infection $<$ 4 months prior to screening.

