- 3) Received any approved, authorized, or investigational direct acting antiviral drug against SARS-CoV-2 for the treatment of COVID-19 $<$ 28 days or $<$ 5 half-lives, whichever is longer, before enrollment.
- 4) CCI [REDACTED]

5) Any of the following abnormal laboratory results at screening:

- a) CCI [REDACTED]
- b) eGFR < CCI [REDACTED]
- c) Serum creatinine: CCI [REDACTED]

Gestational age	Chronological age	Creatinine Value Cutoff in mg/dL
≥ 24 to ≤ 27 weeks	0 to < 28 days	CCI
≥ 28 to ≤ 29 weeks	0 to < 14 days	CCI
≥ 30 to < 32 weeks	0 to < 7 days	CCI
	≥ 7 days to 1 month	CCI
	≥ 1 to < 2 months	CCI
	≥ 2 months to < 1 year	CCI
	0 to < 2 days	CCI
≥ 32 weeks	≥ 2 to < 7 days	CCI
	≥ 7 days to 2 months	CCI
	≥ 2 months to < 1 year	CCI

* Creatinine values CCI [REDACTED]

- 6) CCI [REDACTED].
- 7) CCI [REDACTED].
- 8) CCI [REDACTED].
- 9) CCI [REDACTED]
- 10) CCI [REDACTED]

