6.3.2.4. Clinical Laboratory Assessments

Refer to [Table 1](#) for clinical laboratory assessment time points.

Following laboratory assessments will be performed:

- Hematology: Complete blood count (CBC) with differential
- Comprehensive metabolite panel (Chemistry 14): ALT, albumin, alkaline phosphatase, aspartate aminotransferase (AST), total bilirubin (and neonatal bilirubin for participants aged <14 days and participants presenting with jaundice), blood urea nitrogen and creatinine

(include BUN:Cr ratio, and eGFR using bedside Schwarz formula if \geq 1 year of age), ionized calcium, carbon dioxide, chloride, total serum protein, potassium, sodium

- Urinalysis

The smallest possible blood vials, such as microtainer tubes, must be used for participants weighing < 15 kg.

Clinical laboratory assessments at other days may be conducted if required by clinical need or local practice. The results of all clinical laboratory tests that are performed as part of clinical care, even if not required by the protocol, should be reported.

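### The creatinine stop covers all infants under 1 year, but as printed Table 3 has no cutoff for those born at 24-29 weeks beyond 28 or 14 days of age

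*Protocol*

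**What the plan says.** Section 3.3.1.1 of the Protocol lists two renal reasons for stopping study drug that do not depend on suspected relatedness, divided at the first birthday. From 1 year the rule is "eGFR < 50 mL/min/1.73 m² (≥ 1 year of age) using the Bedside Schwartz formula". Below 1 year it is "Creatinine level above the thresholds described in [Table 3](#) if < 1 year of age".

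Table 3 sets creatinine cutoffs by gestational age (GA) and chronological age. The cutoff values are redacted, but the age rows are legible:

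- GA 24-27 weeks: one row, 0 to under 28 days.
- GA "≥ 28 to ≤ 29 weeks": one row, 0 to under 14 days.
- GA 30 to under 32 weeks, and 32 weeks or more: several rows, the last in each band being "≥ 2 months to < 1 year".

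The table in exclusion 5c (section 4.3) prints the same age rows, beginning with "≥ 24 to ≤ 27 weeks".

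Section 4.2 admits infants under 1 year by two routes that matter here. One is "Cohort 4: ≥ 28 days to < 18 years and weight ≥ 3 kg to < 12 kg", with no GA or birth-weight condition. The other is Cohort 7: 0 to under 56 days of age, GA below 37 weeks and birth weight of at least 1.5 kg.

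**The concern.** The stop rule is written for every participant under 1 year, but it works only through a table that, as printed, does not cover every such participant. If an infant has no row, there is no threshold to be above and the rule cannot act.

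The protocol treats a renal stop that ignores relatedness as a deliberate safeguard. Section 7.7.1.3 says that the eGFR stop applies whether or not the event is considered related. Infants born very early are within the intended population: section 1.1 says "prematurity in infants is also a risk factor for severe disease", and Cohort 7 is reserved for preterm infants. Safety is a primary objective, so a stopping rule that is undefined for some eligible infants would be applied unevenly between sites.

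**Working it through.** The protocol gives no figure to reproduce. The check sets the printed rows against the age and GA limits of the cohorts. GA is read in completed weeks, the first year is days 0-364, and weight is not modelled.

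**1. Days of the first year without a row in Table 3**

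| GA (weeks) | Days covered | Days without a row | Share of 365 |
|---|---|---|---|
| below 24 | none | 365 | 100% |
| 24-27 | 0-27 | 365 − 28 = 337 | 92% |
| 28-29 | 0-13 | 365 − 14 = 351 | 96% |
| 30 or more | 0-364 | 0 | 0% |

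**2. Does the eGFR stop fill the gap?** No. Section 3.3.1.1 limits it to 1 year and above. Section 7.7.1.3 repeats the limit without an age restriction but refers back to 3.3.1.1. Section 6.3.2.4 has the value calculated only from 1 year ("and eGFR using bedside Schwarz formula if" followed by that age).

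**3. Can eligible infants fall in the gap?**

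- Cohort 4 starts at day 28 and sets no GA limit. Days 28-364 (337 days) all lie outside the row for 24-27 weeks and the row for 28-29 weeks. On this reading, every Cohort 4 infant under 1 year born before 30 weeks lacks a printed cutoff. An infant born at 26 weeks, now 4 months old and weighing 5 kg, is an example.
- Cohort 7 spans days 0-55, which is 56 days. For 24-27 weeks, 56 − 28 = 28 days (50%) have no row. For 28-29 weeks, 56 − 14 = 42 days (75%) have none. Both cases also require a birth weight of at least 1.5 kg.

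**4. Would another reading of the table remove the problem?** Three age rows carry no GA label of their own: 7 days to 1 month, 1 to under 2 months, and 2 months to under 1 year. They appear to belong to the 30 to under 32 week band. Suppose they were meant for all infants below 32 weeks. The gap for 24-29 weeks would close, but two rows would then apply to the same infant:

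- 24-27 weeks: days 7-27, that is 27 − 7 + 1 = 21 days.
- 28-29 weeks: days 7-13, that is 13 − 7 + 1 = 7 days.

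So the table has either a gap or an overlap.

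**5. What still protects these infants on treatment?** Section 3.3.1.1 also stops study drug for any related Grade 3 or higher AE, for a confirmed, clinically significant, related Grade 3 or higher laboratory abnormality, and where the investigator judges that continuing is not in the participant's interest. None of these is a fixed renal limit independent of relatedness.

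**The case against.** A reader might infer that these infants have no creatinine-based limit at all, at entry or on treatment, and that infants with impaired renal function could enter and distort the PK results. The documents do not support that.

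- **Entry.** The eGFR exclusion, the lead-in to the serum creatinine exclusion, the table footnote and several other exclusions are redacted. Any of them could cover the ages without a row or exclude these infants. Redacted text cannot be counted as absent, so no entry gap is claimed, and the PK consequence goes with it.
- **Treatment.** The general stops in step 5 remain. What is missing is narrower: an age-specific cutoff that acts regardless of relatedness. The footnote under Table 3 is redacted too and might address the point, but the legible stop sentence refers only to the table's thresholds.
- **Contrast with other children.** It would be wrong to say that all other participants have this limit, since GA below 24 weeks has no row at any age.
- **Layout.** The label for 32 weeks or more sits beside a different age row in each of the two tables as they can be read here, so label positions are uncertain. This stands as a caution, but the alternative reading produces overlapping cutoffs.
- **Reach.** The percentages count days of age, not participants. Cohort 4 needs only 12 evaluable participants across 28 days to under 18 years, and Cohort 7 has no minimum because such participants are rare. The protocol does not say how many would be affected.
- **Timing.** Dose and formulation (section 5.4), PK sampling (section 6.3.5) and blood volumes (Appendix 11.6) for the younger cohorts await an amendment. That lowers the urgency. No section defers the renal tables, however, so the printed rows are current text.

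**Conclusion.** The point holds in a limited form. The stop rule for infants under 1 year and the printed rows of Table 3 do not match. There is no age-specific cutoff for GA 24-27 weeks from 28 days to under 1 year (92% of the first year), for 28-29 weeks from 14 days to under 1 year (96%), or for GA below 24 weeks at any age. Infants in these ranges can meet the age, weight and GA criteria of Cohort 4 and, with sufficient birth weight, Cohort 7. For them, the renal stop that ignores relatedness cannot trigger as printed, while the general stops continue to apply.

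This rests on the literal reading of the rows, on GA in completed weeks, and on the redacted footnote not supplying the missing rule. The number of infants affected is unknown and probably small. It is a safety-rule inconsistency worth correcting before those cohorts open, and it does not show that the trial lacks renal protection.

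**What to change.** Before Cohorts 4 and 7 open, the sponsor should reconcile four items: the stop rule for participants under 1 year in section 3.3.1.1, the rows of Table 3, the rows of the exclusion 5c table, and the cohort definitions in section 4.2. After the edit, every eligible infant under 1 year should fall under exactly one stated rule, with no gap or overlap. If the redacted footnote already settles this, a cross-reference from the stop rule would be enough. How the infants without a row are handled, and any values, are for the sponsor to decide; no cutoff or clinical rule is proposed here.

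The cost is a small edit that can go into the amendment already needed for the younger cohorts. GA is already collected for participants under 1 year (section 6.3.2.5), so no new data are required. A few infants may be handled differently than under the printed table.

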3.3.1.2. Criteria for Early Discontinuation for the Individual Participant From the Study

The participant will be discontinued from the study regardless of whether treatment is ongoing in the following instances:

- Withdrawal of consent/assent
- Death

3.3.2. Criteria for Early Discontinuation of the Study

The study will be discontinued in the following instances:

- Discontinuation of the study at the request of Gilead Sciences (Gilead) or a regulatory agency, institutional review board (IRB), or independent ethics committee (IEC).

3.3.3. Loss to Follow-up

Should the participant fail to return to the investigational site for a scheduled protocol-specific visit, sites will need to make at least 3 attempts by a combination of telephone, email, or mail to contact the participant. Sites must document all attempts to contact the participant. If a participant does not respond within 5 days within the third contact, the participant will be considered lost to follow-up and no additional contact will be required.

3.4. Definitions for Time of Primary Endpoint and End of Study

3.4.1. Primary Endpoint

The date for the last participant visit for the primary endpoint is the date of the last visit to perform assessments for the primary analysis.

3.4.2. End of Study

The end of this study will be the last participant's last observation (or visit).

3.5. Source Data

The source data for this study will be obtained from original records (eg, clinic notes, hospital records, participant charts), central laboratory, local laboratory, and specialty laboratory (for PK data), participant (or caregiver)-reported outcomes, and Interactive Response Technology (IRT). Electronic data capture is not considered source data.

4. PARTICIPANT POPULATION

4.1. Number of Participants and Participant Selection

At least 52 participants will be enrolled into the study including 12 evaluable participants per cohort from Cohorts 1-4 and a minimum of 4 evaluable participants from Cohort 5. Participants in Cohorts 6 and 7 will only be enrolled once ODV exposures have been evaluated from preceding cohort(s) and a dose has been determined. There is no minimum number of participants to be enrolled in Cohorts 6 and 7 due to the rarity of such participants.

4.1.1. Participant Replacement

If necessary, and with Gilead approval, replacement participants may be enrolled if a participant is considered non-evaluable for primary safety and/or PK analysis (Sections 8.3.1.2 and 8.3.1.3). Replacement participants will not be enrolled for participants who discontinued the study due to a study drug-related AE.

4.2. Inclusion Criteria

Participants must meet all of the following inclusion criteria to be eligible for participation in this study:

- 1) Participant or legal guardian willing and able to provide written informed consent prior to performing study procedures. Participants will provide assent, if possible, in accordance with local requirements and investigator's discretion.
- 2) Aged < 18 years who meet one of the following weight criteria and gestational age (GA) criteria where applicable (where permitted according to local law and approved nationally and by relevant IRB or IEC):
 - a) Cohort 1: ≥ 6 years to < 18 years and weight ≥ 40 kg
 - b) Cohort 2: ≥ 6 years to < 18 years and weight ≥ 20 kg to < 40 kg
 - c) Cohort 3: ≥ 2 years to < 18 years and weight ≥ 12 kg to < 20 kg
 - d) Cohort 4: ≥ 28 days to < 18 years and weight ≥ 3 kg to < 12 kg
 - e) Cohort 5: ≥ 14 days to < 28 days of age, GA ≥ 37 weeks and weight ≥ 2.5 kg
 - f) Cohort 6: 0 days to < 14 days of age, GA ≥ 37 weeks and birth weight ≥ 2.5 kg
 - g) Cohort 7: 0 days to < 56 days of age, GA < 37 weeks and birth weight ≥ 1.5 kg
- 3) SARS-CoV-2 infection confirmed by polymerase chain reaction (PCR) or an alternative molecular diagnostic assay ≤ 5 days before screening.

- 4) Initial onset of COVID-19 signs/symptoms \leq 5 days before screening with \geq 1 sign/symptom such as fever, cough, fatigue, shortness of breath, sore throat, headache, myalgia/arthralgia present at screening.
- 5) Presence of \geq 1 characteristic or underlying medical condition associated with an increased risk of developing severe illness due to COVID-19, including:
 - a) CCI [REDACTED]
 - b) CCI [REDACTED]
 - c) CCI [REDACTED]
 - d) CCI [REDACTED]
 - e) CCI [REDACTED]
 - f) CCI [REDACTED]
 - g) CCI [REDACTED]
 - h) CCI [REDACTED]
 - i) CCI [REDACTED]

4.3. **Exclusion Criteria**

Participants who meet *any* of the following exclusion criteria are not eligible to be enrolled in this study:

- 1) Anticipated access to and use of authorized or approved COVID-19 therapies during the current COVID-19 illness $<$ 5 days after screening (therapies including but not limited to nirmatrelvir/ritonavir, molnupiravir, intravenous RDV, monoclonal antibodies).
- 2) Vaccination for SARS-CoV-2 or self-reported history of SARS-CoV-2 infection $<$ 4 months prior to screening.
- 3) Received any approved, authorized, or investigational direct acting antiviral drug against SARS-CoV-2 for the treatment of COVID-19 $<$ 28 days or $<$ 5 half-lives, whichever is longer, before enrollment.
- 4) CCI [REDACTED]

5) Any of the following abnormal laboratory results at screening:

- a) CCI [REDACTED]
- b) eGFR < CCI [REDACTED]
- c) Serum creatinine: CCI [REDACTED]

Gestational age	Chronological age	Creatinine Value Cutoff in mg/dL
≥ 24 to ≤ 27 weeks	0 to < 28 days	CCI
≥ 28 to ≤ 29 weeks	0 to < 14 days	CCI
≥ 30 to < 32 weeks	0 to < 7 days	CCI
	≥ 7 days to 1 month	CCI
	≥ 1 to < 2 months	CCI
	≥ 2 months to < 1 year	CCI
	0 to < 2 days	CCI
≥ 32 weeks	≥ 2 to < 7 days	CCI
	≥ 7 days to 2 months	CCI
	≥ 2 months to < 1 year	CCI

* Creatinine values CCI [REDACTED]

- 6) CCI [REDACTED].
- 7) CCI [REDACTED].
- 8) CCI [REDACTED].
- 9) CCI [REDACTED]
- 10) CCI [REDACTED]

5. STUDY INTERVENTIONS AND CONCOMITANT MEDICATIONS

5.1. Enrollment, Blinding, and Treatment Code Access

5.1.1. Enrollment

Participants who meet eligibility criteria will be enrolled to receive ODV starting on Day 1 and assigned a participant number.

5.1.2. Blinding

Blinding of treatment assignments or data will not be performed in this study.

5.2. Description and Handling of Obeldesivir

5.2.1. Formulation

The ODV tablets are available in strengths of CCI [REDACTED].

The ODV CCI [REDACTED] strength tablets are capsule shaped, debossed with “GSI” on one side and a bisect on the other side, and film-coated white. In addition to the active ingredient, each film-coated tablet contains the following inactive ingredients: microcrystalline cellulose, crospovidone, magnesium stearate, macrogol polyvinyl alcohol graft copolymer, talc, titanium dioxide, glycetyl mono and dicaprylocaprate (glycetyl monocaprylocaprate type I), and polyvinyl alcohol.

The ODV CCI [REDACTED] strength tablets are oval shaped, debossed with “GSI” on one side and “5245” on the other side, and film-coated light yellow. In addition to the active ingredient, each film-coated tablet contains the following inactive ingredients: microcrystalline cellulose, crospovidone, magnesium stearate, macrogol polyvinyl alcohol graft copolymer, talc, titanium dioxide, glycetyl mono and dicaprylocaprate (glycetyl monocaprylocaprate type I), polyvinyl alcohol, and yellow iron oxide.

